## 5.5 Immunogenicity Analyses

### 5.5.1 Anti-drug antibodies

Antidrug antibodies will be measured using a 3-tiered assay approach: screening assay, confirmatory assay and titration assay.

A screening cut point will be determined by the bioanalytical laboratory that will be used to determine the status of ADAb as “Positive Screen” (PS) or “Negative Screen” (NS). For samples presenting ADAb levels as PS, further confirmatory assay will be performed, and the result of which will be reported as either “Positive Immunodepletion” (PI) or “Negative Immunodepletion” (NI). Samples that are confirmed as positive (reported as PI) will be titrated, and the titer (reciprocal dilution factor including minimum required dilution [MRD]: 100) will be reported.

#### ADAb status at any time point:

- An ADAb status of positive (ADAb+) will be concluded for any sample with an ADAb level that is PS and PI;
- An ADAb status of negative (ADAb-) will be concluded for any sample with an ADAb level that is either NS or PS and NI;
- Missing or a non-evaluable sample will be defined as missing;

#### Study participant Classification:

- A study participant will be classified as having ADAb positivity at Baseline if the Day 1, Predose result is ADAb+;
- A study participant will be classified as overall positive if at least one post-Baseline measurement is ADAb+;
- A study participant will be classified as overall negative if at all post-Baseline visits the ADAb status is negative (this includes study participants who have ADAb+ results at Baseline) or only one sample is missing and all other ADAb samples are negative;
- Missing if the study participant has missed more than one ADAb sample and all other available ADAb samples are negative;
- A participant will be classified as having treatment-emergent ADAb positivity when meeting one of the following criteria:
  - The Baseline result is ADAb-, and at least one post-Baseline time point is ADAb+;
  - The Baseline result is ADAb+, and at least one post-Baseline measurement shows a 1.81-fold increase in titer from the Baseline value (the Minimum Significant Ratio [MSR] in healthy study participants).

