### **9.5.2 Immunogenicity analyses**

Bimekizumab ADAb levels will be listed per participant and summarized using summary tables and figures. The number (and percentage) of study participants with first occurrence of treatment-induced ADAb positivity will also be summarized at each postdose visit.

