#### 1.1.2.3 Immunogenicity endpoints

##### 1.1.2.3.1 Other/Exploratory immunogenicity endpoint

The other/exploratory immunogenicity endpoint is:

- Incidence of bimekizumab antidrug antibodies (ADAbs)

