#### Analysis:

Immunogenicity will be assessed through summary tables and figures and listing of individual results by study participant. All analyses will be run on the SS, unless specified otherwise. For all tabulations, percentages will be calculated based on the number of study participants with non-missing data.

- All individual participant-level ADAbs results will be listed by treatment group. This will include the screening assay, confirmatory assay, and titer (if applicable). ADAbs samples that are negative but have drug concentration above the drug tolerance characteristics of the assay will be flagged.
- Number and percentage of participants with a positive and negative ADAbs status will be summarized at the time of each visit and overall, separated by treatment group and for all bimekizumab treated participants.
- In addition, the first occurrence of treatment-emergent ADAbs positivity (based on the definitions above) will be summarized (number and percentage of study participants) at each post-Baseline visit, based on the SS. This tabulation will present the number and percentage of study participants at each post-Baseline visit who fulfill at least one of the above defined criteria for treatment-emergent positivity; study participants will be counted in the numerator based on the earliest visit at which one of these criteria is fulfilled. At other visits, study participants will be counted in the denominator (assuming a measurement is available). For all tabulations, percentages will be based on the number of observations at each visit. This summary will exclude any samples with bimekizumab concentrations confirmed to be above the drug tolerance.

A listing will be presented showing the bimekizumab concentrations and ADAbs measurements in the same output in adjacent columns, based on the SS. The listing will include the bimekizumab concentration, ADAbs status (positive or negative) and screening assay results (PS or NS) and confirmatory assay results if applicable (PI or NI), together with the titer if applicable. Titer values will be reported as <100 or as 100 (Minimum Required Dilution, MRD) and above in the listing. In addition, the time since the administration of study medication will be reported (in days).

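### No overall treatment-emergent ADAb percentage is planned: the only overall figure per arm counts unchanged Baseline positives and drops incompletely sampled participants only when all their results are negative

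*SAP*

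**What the plan says.** The SAP names the endpoint as "Incidence of bimekizumab antidrug antibodies" (1.1.2.3.1, other/exploratory). The protocol objectives tables use equivalent wording. Neither document says which participants are incident cases.

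SAP 5.5.1 then sets up two classifications.

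- **Overall status.** "A study participant will be classified as overall positive if at least one post-Baseline measurement is" ADAb-positive. No condition is placed on Baseline status, titer or missed samples. A participant is overall negative if every post-Baseline sample is negative "or only one sample is missing and all other" samples are negative. The third class is "Missing if the study participant has missed more than one" sample, with all available results negative.
- **Treatment-emergent positivity.** This requires either a negative Baseline and a later positive, or a positive Baseline where "at least one post-Baseline measurement shows a 1.81-fold increase in titer from the Baseline value".

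Under the Analysis heading of 5.5.1, positive and negative status is summarised by visit and overall, per arm and pooled. The denominator rule there is: "For all tabulations, percentages will be calculated based on the number of study participants with non-missing data". Treatment-emergent positivity is summarised only as first occurrence at each post-Baseline visit, with the observations at that visit as denominator and with samples above the assay's drug tolerance excluded. Protocol 9.5.2 likewise plans "first occurrence of treatment-induced ADAb positivity" by postdose visit only.

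**The concern.** Two features of the overall percentage make it hard to read as an incidence.

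First, the SAP distinguishes antibody present before dosing from antibody that appears or rises after it, but gives an overall percentage only for the class that mixes the two. A participant with stable pre-dose reactivity is a case in that row.

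Second, whether an incompletely sampled participant enters the denominator depends on the result. This can raise the reported percentage, by an amount that depends on how many participants have gaps.

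At stake is the summary that readers will take as the ADAb rate for each presentation. The primary bioequivalence decision is not at stake.

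**Working it through.** **1. Applying the rules to test profiles** (six post-dose ADAb samples: Days 13, 28, 56, 84, 112 and 140, from the footnotes to Protocol Table 1-1).

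| Baseline | Post-Baseline samples | Overall status | Treatment-emergent? |
|---|---|---|---|
| Positive | All positive, no 1.81-fold rise | Positive | No |
| Positive | All negative | Negative | No |
| Negative | Four negative, two missed | Missing (leaves denominator) | Not shown |
| Negative | One positive, three negative, two missed | Positive (stays) | Yes |

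Row 1 is the Baseline feature; row 2 limits it to persistent Baseline positives. Rows 3 and 4 have the same gaps but are handled differently.

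**2. Can an overall treatment-emergent percentage be obtained?** Each participant is counted once, at the earliest qualifying visit, so the numerators sum to a count per arm (less anything removed by the drug-tolerance exclusion). The visit percentages have different denominators and cannot be added. No overall denominator is stated.

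**3. Size of the Baseline feature.** The documents give no ADAb rates, so there is no figure of the plan's to reproduce. Assume 60 per arm (the planned arm size), 12 treatment-emergent cases, complete sampling and *b* unchanged Baseline positives:

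- *b* = 0: 12/60 = 20.0%, and the two measures agree.
- *b* = 3: (12 + 3)/60 = 25.0%, against 20.0% treatment-emergent.
- *b* = 6: (12 + 6)/60 = 30.0%, against 20.0%.

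**4. Size of the denominator feature.** Let *p* be the positivity that complete sampling would show, *m* the share missing more than one sample, and *r* the chance that an incomplete participant shows a positive, relative to a complete one. Then

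reported = [p(1 − m) + p·r·m] / [1 − m(1 − p·r)].

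With *m* = 0.10 (assumed) and *p* = 0.30:

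- *r* = 1: (0.27 + 0.03)/(1 − 0.07) = 0.30/0.93 = 32.3%.
- *r* = 0.5: (0.27 + 0.015)/(1 − 0.085) = 0.285/0.915 = 31.1%.
- *r* = 0: 0.27/0.90 = 30.0%, no distortion.

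At *r* = 1, other inputs give:

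- *p* = 0.10, *m* = 0.10: 0.10/0.91 = 11.0%.
- *p* = 0.50, *m* = 0.10: 0.50/0.95 = 52.6%.
- *p* = 0.30, *m* = 0.15: 0.30/0.895 = 33.5%.

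**5. What bounds would show** (60 per arm, 6 incomplete, *p* = 0.30).

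- *r* = 1: 18 positives and 6 × 0.7 = 4.2 Missing. Reported 18/55.8 = 32.3%; bounds 18/60 = 30.0% and 22.2/60 = 37.0%.
- *r* = 0: 54 × 0.30 = 16.2 positives and 6 Missing. Reported 16.2/54 = 30.0%; bounds 16.2/60 = 27.0% and 22.2/60 = 37.0%.

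**6. Which early withdrawals are affected.** The Early Withdrawal Visit repeats the Safety Follow-Up assessments, including an ADAb sample, and Protocol 8.10 asks for a sample at the final visit of withdrawn participants. If that sample fills the Day 140 slot, someone leaving between Days 84 and 112 misses only Day 112 and can still be overall negative; those leaving before Day 84 miss at least two. If it fills no scheduled slot, anyone leaving before Day 112 misses at least two. The SAP does not say which applies.

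**The case against.** A reader might infer that the plan reports something other than its named endpoint. The documents do not support that: incidence is undefined, and reading it as new cases is an interpretation. It is a reasonable one, since the SAP has a treatment-emergent class and the protocol speaks of treatment-induced positivity. What can be said is that the plan does not state which classification is the endpoint.

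A reader might also infer that the Missing rule is an error that removes only non-cases. It can be defended as an evaluability convention: one confirmed positive settles a participant's status, whereas a few negatives among missed samples do not settle absence. The participants removed have unknown status, and the effect falls to zero when incomplete participants show no positives. This stands. What remains is that the percentage can be raised and the plan does not ask for the Missing count to be shown.

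The 10% used above is borrowed. In the protocol and SAP it is the allowance for dropout and non-evaluable participants in the bioequivalence sample size, not a rate of missed ADAb samples, and withdrawn participants may be replaced.

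Nor do the documents support reading this as a biased test between presentations. The objective is to assess immunogenicity, and no between-arm ADAb test or interval is planned. The denominator effect of 0 to 2.3 points is also small beside the binomial standard error at 60 per arm and 30%: √(0.3 × 0.7/60) = 5.9 points.

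Finally, the treatment-emergent count can largely be recovered by summing, and individual results are listed. What is missing is a summary row, not data.

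**Conclusion.** The point holds as a minor reporting gap. The plan gives an overall percentage for a class that includes unchanged Baseline positives, and none for treatment-emergent positivity, for an endpoint called incidence. The Missing rule can also raise that percentage: a true 30% becomes 30.0% to 32.3% if 10% of participants miss more than one sample. The Baseline feature adds the share of persistent, unchanged Baseline positives, for example 5 points for 3 of 60. Both sizes rest on assumed rates. With no persistent Baseline positives and no gaps, overall positive and treatment-emergent percentages coincide.

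The bioequivalence conclusion does not use this percentage. One sensitivity analysis in SAP 5.4.2.3 selects participants by post-Baseline ADAb status, but that is an individual classification and not the primary decision.

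**What to change.** In SAP 5.5.1:

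1. Name treatment-emergent positivity, by the SAP's existing definition, as the incidence endpoint.
2. Add one overall row per arm with its number and percentage. State the denominator and whether the drug-tolerance exclusion applies to this row.
3. Label overall positive status as post-Baseline prevalence.
4. Show the Missing count per arm, with the percentage recalculated counting Missing as all negative and as all positive. Confirmed positives stay in the figure.
5. Say whether an Early Withdrawal ADAb sample fills a scheduled slot when missed samples are counted.

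The cost is a few sentences, one table row and a count with two bounds. No new samples or assays are needed. Under the SAP Introduction, a changed analysis definition before database lock calls for a SAP amendment; additional analyses after lock are described in the study report with their rationale.

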#### Analysis:

Immunogenicity will be assessed through summary tables and figures and listing of individual results by study participant. All analyses will be run on the SS, unless specified otherwise. For all tabulations, percentages will be calculated based on the number of study participants with non-missing data.

- All individual participant-level ADAbs results will be listed by treatment group. This will include the screening assay, confirmatory assay, and titer (if applicable). ADAbs samples that are negative but have drug concentration above the drug tolerance characteristics of the assay will be flagged.
- Number and percentage of participants with a positive and negative ADAbs status will be summarized at the time of each visit and overall, separated by treatment group and for all bimekizumab treated participants.
- In addition, the first occurrence of treatment-emergent ADAbs positivity (based on the definitions above) will be summarized (number and percentage of study participants) at each post-Baseline visit, based on the SS. This tabulation will present the number and percentage of study participants at each post-Baseline visit who fulfill at least one of the above defined criteria for treatment-emergent positivity; study participants will be counted in the numerator based on the earliest visit at which one of these criteria is fulfilled. At other visits, study participants will be counted in the denominator (assuming a measurement is available). For all tabulations, percentages will be based on the number of observations at each visit. This summary will exclude any samples with bimekizumab concentrations confirmed to be above the drug tolerance.

A listing will be presented showing the bimekizumab concentrations and ADAbs measurements in the same output in adjacent columns, based on the SS. The listing will include the bimekizumab concentration, ADAbs status (positive or negative) and screening assay results (PS or NS) and confirmatory assay results if applicable (PI or NI), together with the titer if applicable. Titer values will be reported as <100 or as 100 (Minimum Required Dilution, MRD) and above in the listing. In addition, the time since the administration of study medication will be reported (in days).

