#### 5.4.2.3 Sensitivity analysis

The following sensitivity analyses will be performed following the same model as described for the primary analysis (Section 5.4.2.1):

1. Including main effect of site
2. Including both main effect of site and site-by-treatment interaction
3. Based on all nonpositive ADAb study participants (defined as any positive ADAb observed post-Baseline)
4. Including body weight at Day -1 as covariate
5. Corrected for measured protein content:

For compliance with Canadian Health ministry guidance, AUC and  $C_{max}$  ratio estimates and 90% CIs will be also presented as corrected for measured protein content (potency). A correction factor (CF) will be obtained as the ln-transformed ratio of the percent protein content (Reference/Test). Then, this factor will be added to the difference in LSMS to obtain, by exponentiation, the corrected AUC and  $C_{max}$  geometric mean ratios and the corresponding 90% CIs.

For a given Reference/Test, the correction factor will be calculated using the below formula:

$$CF = \ln\left(\frac{\% \text{ Measured Content Reference}}{\% \text{ Measured Content Test}}\right) \quad [3]$$

The corrected ratio estimate for the PK parameter (AUC or  $C_{max}$ ) is calculated using the below formula:

$$\text{Ratio} = 100 \times \exp(LSM \text{ difference} + CF) \quad [4]$$

Where,

$$LSM \text{ difference} = LSM(\text{Test}) - LSM(\text{Reference}) \quad [5]$$

The corrected 90% CI for the ratio is obtained using the below formula:

$$90\% \text{ CI} = 100 \times \exp[(LSM \text{ difference} + CF) \pm t_{0.05,df} \times se(LSM \text{ difference})] \quad [6]$$

6. Including all excluded and available PK parameters

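### SAP 5.5.1 drops confirmed ADAb positives above drug tolerance from the first-occurrence table, so treatment-emergent cases can be lost or shown late

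*SAP*

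**What the plan says.** SAP 5.5.1 sets sample status from the assay result alone. Positive means screened positive and confirmed. Negative is a "level that is either NS or PS and NI", whatever the drug concentration. A further line reads "Missing or a non-evaluable sample will be defined as missing", but non-evaluable is not defined and not linked to drug tolerance.

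The participant definitions follow. One post-Baseline positive makes a participant overall positive. A Baseline-negative participant with any post-Baseline positive is treatment-emergent positive; a Baseline-positive one needs a 1.81-fold titer rise. Neither definition has a tolerance condition.

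Three outputs use these results:

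- **Listing:** "ADAbs samples that are negative but have drug concentration above the drug tolerance characteristics of the assay will be flagged". Only negatives are flagged.
- **Status table:** "Number and percentage of participants with a positive and negative ADAbs status will be summarized at the time of each visit and overall". No tolerance rule is given.
- **First-occurrence table:** it is said to rest on the definitions above. Each participant enters once, at the first visit that meets a criterion, and percentages use the observations available at that visit. Then comes the restriction: "This summary will exclude any samples with bimekizumab concentrations confirmed to be above the drug tolerance".

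Protocol 9.5.2 plans the first-occurrence summary without any such exclusion, and SAP 6.2 (changes to protocol-planned analyses) records none.

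**The concern.** Circulating drug can mask antibodies, so it casts doubt on a negative result. It gives no comparable reason to doubt a result that was positive and confirmed despite the drug. The listing rule follows this logic, because it flags negatives only. The first-occurrence rule does not: it removes every sample above tolerance, including confirmed positives that the section's own definitions count.

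The status table has the opposite weakness. It accepts negatives above tolerance as ordinary negatives.

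At stake are the number of treatment-emergent participants shown and their time of onset, and whether two tables built from the same samples can be reconciled. ADAb incidence is an endpoint of the study, though an other/exploratory one.

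**Working it through.** The plan states no figure on this point, so there is none to reproduce. The check sets the rules side by side and then adds an illustration.

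**1. Same participant, different outputs**

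| Participant | SAP definitions | Status table | First-occurrence table |
|---|---|---|---|
| Baseline-negative; confirmed positive on Days 13 and 28 only, both above tolerance | Overall positive, treatment-emergent | Positive on Days 13 and 28 and overall | Absent |
| Baseline-negative; positive on Day 28 (above tolerance) and Day 84 (below) | Overall positive, treatment-emergent | Positive at both visits and overall | Entered on Day 84, 56 days late |
| Baseline-negative; true antibody masked on Day 28, no positive elsewhere | Overall negative | Negative | Day 28 sample dropped |
| Baseline-positive, no 1.81-fold titer rise | Overall positive, not treatment-emergent | Positive | Absent, by design |

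The first two rows are the defect. The exclusion shrinks the set of samples in which at least one positive is sought, so the cumulative count of first occurrences can only fall or stay equal. Predose samples should contain no bimekizumab, because earlier assignment to it is an exclusion criterion (protocol 5.2), so Baseline status is not affected.

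**2. Which visits are exposed**

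Inputs: half-life about 28 days (protocol 4.2); ADAb samples on Days 13, 28, 56, 84, 112 and 140 (protocol 1.3). In the terminal phase, the level relative to Day 28 is 0.5^((day − 28)/28):

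- Day 56: 50%
- Day 84: 25%
- Day 112: 12.5%
- Day 140: 6.25%

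Any exclusion therefore falls mainly on the early visits.

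**3. Illustration at one visit**

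The number per arm, 60, is from SAP 3. The rest are assumptions: true ADAb prevalence p = 20%; share of samples above tolerance among ADAb-negatives a− = 60%, and among ADAb-positives a+ = 20%, 60% or 80%; probability of detection above tolerance s = 0.5; no false positives. One visit is taken in isolation.

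This gives 60 × 0.20 = 12 true positives and 48 true negatives, of whom 48 × 0.40 = 19.2 are below tolerance.

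- Status rate = [12(1 − a+) + 12·a+·s]/60
- First-occurrence rate, excluded samples leave numerator and denominator = 12(1 − a+)/[12(1 − a+) + 19.2]
- First-occurrence rate, excluded samples leave the numerator only = 12(1 − a+)/60

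| a+ | Status table | First occurrence, both | First occurrence, numerator only |
|---|---|---|---|
| 20% | (9.6 + 1.2)/60 = 18.0% | 9.6/28.8 = 33.3% | 16.0% |
| 60% | (4.8 + 3.6)/60 = 14.0% | 4.8/24.0 = 20.0% | 8.0% |
| 80% | (2.4 + 4.8)/60 = 12.0% | 2.4/21.6 = 11.1% | 4.0% |

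The status rate never exceeds the true 20%. With s varied from 0 to 1 over these values of a+, it runs from 4.0% to 20.0%. The first-occurrence percentage falls on either side of 20% when excluded samples leave the denominator, as the SAP wording suggests they do. Its count of positives is lower than the number detected in every row (4.8 against 8.4 when a+ = 60%).

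**4. Does dropping only the negatives cure it?**

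No. At a+ = 60%, that gives 8.4/(8.4 + 19.2) = 8.4/27.6 = 30.4% against a true 20%. With everyone kept in the denominator, the visit reads:

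- positive: 8.4/60 = 14.0%
- inconclusive: (3.6 + 28.8)/60 = 54.0%
- negative: 19.2/60 = 32.0%

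This does not recover the true rate, but it shows how much is unknown.

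**The case against.** The best defence of the rule is that it is symmetric. Removing all samples above tolerance, whatever their result, gives a percentage among evaluable samples, and that is unbiased when drug level is unrelated to ADAb status (the 20.0% row). This stands as far as it goes, and it is why dropping negatives alone would be worse. But it rests on an equality that nothing in the documents supports, and it does not help a table of first occurrence, where losing the earliest positive misdates or deletes the event.

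Three further points stand. The listing places concentration, status and titer side by side, so a dropped positive can be found. The two tables differ partly by design, as the last row of the first table shows. The endpoint is exploratory, and the tolerance level, concentrations and ADAb rate are all unknown.

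Two stronger readings are tempting, but the documents do not support them:

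- **A reader might infer that ADAb incidence as a whole is biased down by the exclusion.** The exclusion applies to one table. The overall status table still counts every participant with a detected post-Baseline positive, and the direction for per-visit first-occurrence percentages is not fixed.
- **A reader might infer that sensitivity analysis 3 is distorted.** That group is "Based on all nonpositive ADAb study participants" and rests on post-Baseline positivity, which the exclusion does not touch. A participant moved from negative to inconclusive is still nonpositive, so on the plain wording nobody changes group.

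**Conclusion.** The point holds in a limited form. As written, the first-occurrence table discards confirmed positives that SAP 5.5.1 itself defines as treatment-emergent. Participants can vanish from it or be given a later onset, and its cumulative count can only fall or stay equal. Separately, the status table treats negatives above tolerance as true negatives, so, leaving aside assay false positives, its rate is at or below the true one.

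The size cannot be computed from the documents. It is nil if no sample exceeds tolerance, and the percentages above only illustrate assumed values. The primary bioequivalence analysis is unaffected. This is a modest but definite correction to an exploratory output.

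**What to change.** In SAP 5.5.1:

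1. In the first-occurrence table, count every confirmed positive that meets a treatment-emergent criterion, whatever the drug concentration in the sample.
2. In the by-visit and first-occurrence tables, show ADAb-negative samples above tolerance as a separate inconclusive category.
3. Keep inconclusive samples in the denominator, and say so.
4. State that inconclusive is not missing. Under the participant classification, more than one missed sample with all others negative makes a participant missing. If two or more early visits were relabelled as missing, many non-positive participants would leave the overall denominator and the percentage would rise artificially.
5. State the tolerance level of the assay.

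The cost is wording and table shells only: no new samples and no change to sample size. The concentrations are already to be listed beside the ADAb results. The small downside is that some results now shown as negative become inconclusive.
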